C-SSRS	Columbia-Suicide Severity Rating Scale
CDR-SB	Clinical Dementia Rating - Sum of Boxes

Term	Definition
CFI	Cognitive Function Index
cLDA	constrained longitudinal data analysis
CN	conventional
COVID	coronavirus disease
COVID-19	coronavirus disease 2019
CRF	case report form
CSF	cerebrospinal fluid
CTR	Clinical Trial Registry
DBL	direct bilirubin levels
DPM	disease progression model
DPR	disease progression ratio
DSMB	Data Safety Monitoring Board
ECG	electrocardiogram
FCSRT	free and cued selective reminding test
GGT	gamma-glutamyl transferase
HABS	Harvard Aging Brain Study
ITT	intent-to-treat
IPTW	inverse probability of treatment weighting
IV	intravenous
Lilly	Eli Lilly and Company
LY	LY2062430
LZAZ	H8A-MC-LZAZ
MAR	missing-at-random
MedDRA	Medical Dictionary for Regulatory Activities
MI	multiple imputation
mITT	modified intent-to-treat

Term	Definition
MNAR	missing-not-at-random
MMRM	mixed-effects model repeated measures
MMSE	Mini-Mental State Examination
MRD	minimal residual disease
MRI	magnetic resonance imaging
MSM	marginal structural models
NAb	neutralizing antibody
NAb+	neutralizing antibody positive
NCS	Natural Cubic Spline
NIA	National Institute on Aging
OLE	Open-label extension
p-tau	phosphorylated tau
PACC	Preclinical Alzheimer Cognitive Composite
PC	placebo-controlled
PET	positron emission tomography
PR	PR interval on the ECG
PRO	participant-reported outcome
PT	preferred term
QRS	the interval that denotes depolarization of the right and left ventricles of the heart
QR	QR interval on the ECG
QT	QT interval on the ECG
QTc	corrected QT interval
QTcF	Fridericia's corrected QT interval
RUI-B	Resource Use Inventory, Brief
SAE	serious adverse event
SAP	statistical analysis plan

Term	Definition
SD	standard deviation
SI	International System of Units
SUVr	standardized uptake value ratio
TBL	total bilirubin levels
TE	treatment-emergent
TE ADA	treatment-emergent ADA
TE ADA+	treatment-emergent ADA positive
TE ADA-	treatment-emergent ADA negative
TEAE	treatment-emergent adverse event
trt	treatment group
ULN	upper limit of normal
usubjid	subject id, unique identifier of each participant
vMRI	volumetric magnetic resonance imaging
WHO	World Health Organization
y	measurement of the PACC

4. Revision History

Statistical Analysis Plan (SAP) Version 1 was approved 27 November 2013 and SAP version 2 was approved 14 January 2019.

SAP Version 3 was approved prior to any unblinded efficacy analyses involving data from Study LZAZ (A4) being conducted and includes the following revisions:

- Added language introducing COVID-19 pandemic interruption and hiatus
- Primary outcome model was changed from MMRM to cLDA-NCS model
- APOE4 carrier status, a stratification variable for randomization in the study, was added to the primary analysis model and secondary/sensitivity analyses.
- Added sensitivity analyses of PACC with MMRM and disease progression model (DPM)
- Analyses for CDR Global Score added to analysis plan.
- Addition of analyses to look at the effect of increasing dose.
- Further description of the Cogstate Composite Scores
- Removed Section 7.9.2.2. Constrained Longitudinal Data Analysis of Slopes as the NCS model will address this question.

SAP Version 2 was approved prior to any unblinded efficacy analyses involving data from Study LZAZ (A4) being conducted and included the following revisions:

- Added delayed-start efficacy analyses for the open-label extension period that was added as part of the Study LZAZ (A4) protocol amendment (c).
- Added safety analyses for the open-label extension
- Modified the description of the analyses to account for the option of increasing the solanezumab dose to 1600 mg
- Changed the study duration from 3.25 years to 4.5 years
- Changed the Gatekeeping Strategy for multiple comparisons based on the FDA feedback to assess the study's weight of evidence
- Changed the sensitivity analyses
- Added subgroup analyses for dose

5. A constrained Longitudinal Data Analysis (cLDA) Natural Cubic Spline (NCS) analysis of the primary outcome measure, the Preclinical Alzheimer Study Objectives

5.1. Primary Objective

The primary objective of this study is to test the hypothesis that solanezumab, administered as an IV infusion every 4 weeks for 4.5 years, will slow cognitive decline as compared with placebo in participants with preclinical AD. The primary objective will be assessed using a constrained Longitudinal Data Analysis (cLDA) Natural Cubic Spline (NCS) analysis (referred to as NCS henceforth) of the primary outcome measure, the Preclinical Alzheimer Cognitive Composite (PACC), a composite that is primarily weighted on episodic memory and executive function tests, in which the specific hypothesis is that the cognitive decline at 240 weeks will be significantly less for solanezumab than for placebo.

The PACC will be composed of 4 components: the total score from the free and cued selective reminding test (FCSRT), the delayed paragraph recall on the logical memory IIa test from the Wechsler Memory Scale, the digit-symbol substitution test from the Wechsler adult intelligence scale-revised, and the MMSE total score. Specifically, for the FCSRT, the total will be the sum of the free and cue score plus the free recall score, resulting in a total from 0 to 96. Each component score is converted to a z-score by subtracting the baseline mean for that component and dividing by the baseline standard deviation for that component. The PACC is the sum of the four resulting z-scores.

5.2. Secondary Objectives

The secondary objectives of the study are as follows:

- To test the hypothesis that solanezumab will slow the decline of perceived cognitive function and performance of everyday activities, as compared with placebo, using NCS analysis of the Cognitive Function Index (CFI).
- To assess whether decline in activities of daily living begins by the end of the treatment period, and if so, whether an effect of solanezumab, compared with placebo, can be detected using NCS analysis of the ADCS-Activities of Daily Living (ADL) Prevention Questionnaire.
- To assess the relationship between treatment effect and time using the PACC.
- To test the hypothesis that solanezumab reduces brain amyloid burden, as compared with placebo, as assessed using florbetapir positron emission tomography (PET) imaging.
- To assess effects of solanezumab on CSF and plasma concentrations of total tau peptides and phosphorylated tau peptides (p-tau).
- To assess effects of solanezumab on CSF concentrations of A β .
- To investigate the effect of treatment with solanezumab on volumetric MRI.

- To assess the safety of solanezumab versus placebo treatment, including AEs and immunogenicity.

The secondary objectives of the open-label period of the study are as follows:

- To assess the persistence of effect of solanezumab treatment in participants with preclinical AD. That is, to test the hypothesis that participants originally randomized to receive placebo and later switched to solanezumab at the start of the open-label period do not “catch up” to participants originally randomized to receive solanezumab in the placebo-controlled period, using a randomized/delayed-start analysis. The main efficacy objective of the open-label period will be an interim randomized/delayed-start analysis of the PACC at the time of database lock for the placebo-controlled period using data available up to 2 years in the open-label period.
- To test the hypothesis that solanezumab will continue to slow the decline associated with preclinical AD during open-label treatment, comparing participants initially randomized to solanezumab with participants initially randomized to placebo in the placebo-controlled treatment period, using randomized/delayed-start analysis of the MMSE, CDR-SB, C3, CFI, and the ADCS-ADL Prevention Questionnaire.

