6.2. Secondary Objectives

The secondary objectives of the placebo-controlled period of the study are as follows:

- To test the hypothesis that solanezumab will slow the decline of perceived cognitive function and performance of everyday activities, as compared with placebo, using an NCS analysis of the Cognitive Function Index (CFI).
- To assess whether decline in activities of daily living begins by the end of the treatment period, and if so, whether an effect of solanezumab, compared with placebo, can be detected using an NCS analysis of the ADCS-Activities of Daily Living (ADL) Prevention Questionnaire.
- To assess the relationship between treatment effect and time using the PACC.
- To test the hypothesis that solanezumab reduces brain amyloid burden, as compared with placebo, as assessed using florbetapir positron emission tomography (PET) imaging.
- To assess effects of solanezumab on CSF and plasma concentrations of total tau peptides and phosphorylated tau peptides (P-tau).
- To assess effects of solanezumab on CSF concentrations of A β .
- To investigate the effect of treatment with solanezumab on volumetric MRI.
- To assess the safety of solanezumab versus placebo treatment, including AEs and immunogenicity.

The secondary objectives of the open-label period of the study are as follows:

- To assess the persistence of effect of solanezumab treatment in participants with preclinical AD. That is, to test the hypothesis that patients originally randomized to receive placebo and later switched to solanezumab at the start of the open-label period do not “catch up” to patients originally randomized to receive solanezumab in the placebo-controlled period, using a randomized/delayed-start analysis. The main efficacy objective of the

open-label period will be an interim randomized/delayed-start analysis of the PACC.

- To test the hypothesis that solanezumab will continue to slow the decline associated with preclinical AD during open-label treatment, comparing participants initially randomized to solanezumab with participants initially randomized to placebo in the double-blind treatment period, using randomized/delayed-start analysis of the MMSE, CDR-SB, C3, CFI, and the ADCS-ADL Prevention Questionnaire.

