7.1.5. Open-Label Extension Period

Subjects who complete the placebo-controlled period will be eligible to participate in the open-label extension period. Subjects participating in the open-label period will receive open-label solanezumab treatment for varying durations. While all subjects will receive solanezumab treatment during the open-label period, subjects, site personnel, and study teams will remain blinded to initial treatment assignment in the placebo-controlled period until the conclusion of the study.

The open-label period uses a common close design such that all subjects will complete the period at the same time: when analyses of the placebo-controlled period are completed and reviewed. Given the common close design, the overall duration of treatment for each patient will differ. If the study is positive, participants may be offered the opportunity to continue in the open-label period beyond the common close. Subjects who opt to participate in the open-label period should begin the open-label period at Visit 66 (Week 240) after completion of all Visit 66 tests and procedures. However, subjects may enter the open-label period of the study and receive their first open-label infusion of study drug up to 12 weeks following completion of the placebo-controlled period Visit 66 assessments and procedures. In extenuating circumstances, subjects may enter the open-label period after 12 weeks with the approval of a Medical Monitor and/or Project Director. See the Study Schedule ([Attachment 1](#)) for the timing of events and measures to be assessed. Procedures for some visits may take more than 1 day.

Subjects who choose not to participate in the open-label period will not receive any study medication after the last infusion visit for the placebo-controlled period (Week 236). Sites must obtain approval from the Coordinating Center before engaging in open-label activities.

If the open-label period is extended beyond Visit 117, participants who complete Visit 117 before implementation of the protocol amendment that includes additional visits will be allowed to resume study visits once available at their site.

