The noninferiority margin for this hypothesis is specified as 50% of the treatment difference observed at the end of the placebo-controlled period. The hypothesis will be tested by constructing a 90% one-sided CI of the difference in LS means at the last visit in the open-label period. If the lower limit of the CI rules out the difference that would have been obtained if 50% of the observed difference had been lost, the disease progression for the treatment groups will be considered parallel, indicating that the treatment effect is independent of symptomatic effects. The interim noninferiority analysis of the PACC up to Week 336 in the open-label period will be considered the main efficacy analysis for the open-label period.

In addition to the noninferiority test, superiority of early-start subjects compared with delayed-start subjects at the 336-week analysis in the open-label period will also be assessed. The PACC, ADCS-ADL Prevention Questionnaire, CDR-SB, C3, and CFI will be analyzed.

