6.1. Summary of Study Design

Study A4 is a multicenter, randomized, double-blind, placebo-controlled, Phase 3 study comparing solanezumab with placebo for 240 weeks in approximately 1150 participants ages 65 to 85 years old with preclinical AD, defined as having evidence of brain amyloid pathology without clinically evident cognitive impairment at screening. Participants who met entry criteria were randomized in a 1:1 ratio (approximately 575 per treatment arm) to solanezumab or placebo once every 4 weeks. Participants were randomized within the site by education – high (13 or more years) or low (12 or less years) and the presence of one or more apolipoprotein E gene (APOE) ϵ 4 alleles (yes, no). The primary hypothesis being tested is that the cognitive decline at the end of the placebo-controlled period will be significantly less for solanezumab than for placebo. Participants completing the placebo-controlled period of the study can opt to participate in the open-label period of the study that will last for up to 204 weeks or until the primary analyses of the placebo-controlled period of the study are completed and reviewed.

At the beginning of the COVID-19 pandemic, a hiatus was implemented to allow participants to pause study activities without missing visits and resume when COVID safety mitigations were in place (for example, vaccines, home infusions, etc.). The hiatus extended the end of the placebo-controlled period for up to 9 months and the placebo-controlled period will be administratively closed in December 2022.

Figure A4.SAP.1 illustrates the study design.

Abbreviation: V = visit.

Figure A4.SAP.1. Illustration of study design for Clinical Protocol A4.

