6.2. Determination of Sample Size

In order to develop an appropriate measure of cognitive decline in a preclinical population, we tested several combinations of measures using data from longitudinal studies in clinically normal populations, including the ADNI; the AIBL; the ADCS-PI trial; and the HABS.

Sample size and power at 4.5 years (240 weeks) for the PACC were estimated using data from ADNI and HABS. Estimates were obtained by applying appropriate assumptions regarding treatment difference, SD, and attrition for a 4.5-year study in a preclinical AD population. In ADNI, the difference in the composite change between participants with and without elevated brain amyloid at 240 weeks was 2.13 (SD=2.85). Similarly, in HABS, the difference in the composite change between participants with and without elevated brain amyloid at 240 weeks was 2.66 (SD=3.08). Given the ADNI-derived estimate of SD at 240 weeks of SD=2.85 and 30% attrition, the total N=1150 provides 80% power (5% 2-sided alpha) to detect a treatment difference of 0.532 points or $0.532/2.13 = 24.9\%$ of the amyloid group difference. Similarly, based on the HABS estimate of SD at 240 weeks of SD=3.08, the study has 80% power to detect a treatment difference of 0.570 points or $0.570/2.66 = 21.4\%$ of the amyloid group difference.

For the open-label period, the estimated mean PACC difference between cognitively normal participants with and without elevated brain amyloid at 336 weeks is 2.95 (SD=3.77) based on ADNI and 4.74 (SD=3.99) based on HABS. Accounting for the administrative censoring that will be induced by the common close design of the open-label period, and assuming an overall attrition rate of 30%, about 266 PACCs are expected to be available at 336 weeks. The visit-to-visit correlation is estimated to be about 0.5. Under these pilot estimates, 266 PACCs at 336 weeks would provide 80% power to detect a randomized group (early-start vs delayed-start treatment with solanezumab) difference of about 0.9 PACC points. This change of 0.9 PACC points reflects 30% of the difference between amyloid-positive and -negative participants based on ADNI, and 20% of that difference based on HABS.

Sample size for the study was determined assuming an MMRM analysis prior to the interruption caused by the COVID-19 pandemic. Applying the NCS approach in simulated trials with a COVID-19 pandemic interruption suggests the study has 94% power to detect an effect size of 0.75 PACC points at 240 weeks.

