7.9.3.2. Delayed-Start Analysis of PACC

The main efficacy analysis of the open-label period is to test for disease progression between treatment groups from the end of the placebo-controlled period at Week 240 to the time point in the open-label study period at Week 336 as assessed by the PACC. Comparisons will be made between participants who started solanezumab at the beginning of the placebo-controlled period (early start) and those who started solanezumab at the beginning of the open-label period (delayed start).

In the following description, the difference between solanezumab and placebo at the end of the placebo-controlled period will be denoted Δ_1 ; the difference between early-start and delayed-start solanezumab at the time point of interest in the open-label period will be denoted Δ_2 . Note that Δ_1 is the effect obtained from the MMRM analysis of the placebo-controlled period. The primary delayed-start efficacy measure will be analyzed using estimates from MMRM models, in which three specific hypotheses are tested:

1. Δ_1 is statistically significantly greater than 0.
2. Δ_2 is statistically significantly greater than 0.
3. 90% one-sided confidence limit of $\Delta_2 - 50\% \Delta_1$ is greater than 0.

The change from baseline (prior to the initiation of treatment in the placebo-controlled period) at each visit during both the placebo-controlled period and the open-label period (at the visits when the PACC is assessed) will be the dependent variable. The model for the fixed effects will include terms for: baseline PACC, treatment, visit, treatment-by-visit interaction, education, APOE4 Carrier Status (yes/no), baseline florbetapir cortical SUV_r, and age at baseline. Visit will be considered a categorical variable with values equal to the visit numbers at which the PACC was assessed. An unstructured covariance matrix will be used to model the within-participant variance–covariance errors. If the unstructured covariance structure matrix results in a lack of convergence, the following tests will be used in sequence:

- heterogeneous Toeplitz covariance structure
- heterogeneous autoregressive order 1 covariance structure
- heterogeneous compound symmetry covariance structure
- compound symmetry covariance structure

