The first hypothesis will be tested using an estimate of Δ_1 obtained from an MMRM model fit using data from all randomized participants through week 240 (the end of the placebo-controlled period). The second hypothesis will be tested using an estimate of Δ_2 obtained from an MMRM including data from all randomized participants through week 336 (96 weeks of open-label period).

The noninferiority margin for this hypothesis is specified as 50% of the treatment difference observed at the end of the placebo-controlled period. The hypothesis will be tested by constructing a 90% one-sided confidence interval of the difference in least-squares means at the last visit in the delayed-start period. If the lower limit of the confidence interval rules out the difference which would have been obtained if 50% of the observed difference had been lost, the disease progression for the treatment groups will be considered parallel in the open-label period, suggesting the treatment effect is independent of symptomatic effects and that solanezumab has a persistent effect on disease course.

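### SAP 5.2 times the main open-label analysis (Week 336 PACC) at the placebo-controlled database lock, a trigger the current protocol lacks, so Week 336 PACCs collected between the lock and the common close would be left out

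*SAP*

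**What the plan says.** SAP 5.2 (Secondary Objectives, open-label period) makes the main open-label efficacy objective an interim delayed-start analysis of the PACC, performed "at the time of database lock for the placebo-controlled period using data available up to 2 years in the open-label period".

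Protocol 6.2 has the same objective but no timing clause: the main efficacy objective of the "open-label period will be an interim randomized/delayed-start analysis of the PACC". Protocol 11.2.10 repeats the status of the analysis, again without a date or trigger: "The interim noninferiority analysis of the PACC up to Week 336 in the open-label period will be considered the main efficacy analysis".

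The method is in SAP 7.9.3.2, which compares the groups from Week 240 "to the time point in the open-label study period at Week 336 as assessed by the PACC". That section gives the model and the hypotheses but no data cut-off.

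On how long data collection lasts, Protocol 7.1.5 ends the open-label period for everyone together, at the point when the placebo-controlled results have been analysed and reviewed (the common close). It adds: "If the study is positive, participants may be offered the opportunity to continue in the open-label period beyond the common close". Attachment 1 of the protocol schedules open-label PACCs every 24 weeks, with Week 336 at Visit 90.

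SAP 6.2 and Protocol 11.1 plan on the basis that, after 30% attrition and the censoring caused by the common close, "about 266 PACCs are expected to be available at 336 weeks".

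**The concern.** The two documents disagree on when the main open-label analysis takes place, and the SAP version is the less favourable one. A database lock necessarily precedes the completion and review of the analyses made from it. Participants therefore go on reaching Visit 90 after the lock, and those assessments are made whatever the SAP says. A cut-off at the lock excludes them from the one analysis for which Week 336 was chosen.

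The timing also needs to be settled in advance. Under Protocol 11.2.10 the delayed-start analysis goes ahead only if the Week 240 contrast is significant. If the SAP and protocol still point to different cut-offs then, the choice between them would be made with the primary result known.

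**Working it through.** **Step 1. The time point.** Week 336 − Week 240 = 96 weeks of open-label follow-up.

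**Step 2. Which assessments depend on the cut-off.** Let L be the lock date and C the common close, with C later than L. A participant still in the study has a Week 336 PACC by date D if Week 240 was passed by D − 96 weeks (taking visits on schedule). So:

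- count at lock = retained participants with Week 240 on or before L − 96 weeks;
- count at close = retained participants with Week 240 on or before C − 96 weeks;
- loss from the SAP 5.2 timing = retained participants whose Week 240 falls between those two dates.

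The loss cannot be negative. It is zero only if nobody falls in that interval.

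**Step 3. Whether the loss can be sized.** It needs L, C and the distribution of Week 240 dates. SAP 6.1 gives one relevant calendar date, the administrative close of the placebo-controlled period in December 2022, and says the COVID-19 hiatus moved the end of that period by up to 9 months. Since 96 × 7 = 672 days:

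- a participant reaching Week 240 in December 2022 is due at Week 336 in October or early November 2024;
- a Week 336 PACC by the end of December 2022 requires Week 240 to have been passed by about the end of February 2021.

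This shows how long the lag is. It does not show how many people fall in the interval, because L, C and accrual are not given.

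**Step 4. What the planning count says.** Retained = 1150 × (1 − 0.30) = 805.

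- 266 as a total: 266/805 = 33.0%.
- 266 per arm: 532/805 = 66.1%.

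SAP 6.2 ties the 266 to common-close censoring. It is therefore a count at C, and by Step 2 the count at L is no higher.

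**Step 5. Whether the stated power shows which reading is meant.** SAP 6.2 states 80% power for about 0.9 points, with SD 3.77 (ADNI) or 3.99 (HABS) and visit-to-visit correlation 0.5. A plain two-sample calculation uses power = Φ(0.9/SE − 1.96).

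| Reading | SE (ADNI / HABS) | Power (ADNI / HABS) |
|---|---|---|
| 266 total, SE = SD × √(4/266) | 0.462 / 0.489 | 49.5% / 45.2% |
| 266 per arm, SE = SD × √(2/266) | 0.327 / 0.346 | 78.6% / 73.9% |

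A repeated-measures calculation with 266 as a total credits the earlier visits. It assumes 24-weekly visits, equal correlation 0.5, and linear loss to 70% at Week 240 and then to 266 at Week 336. It gives 67.3% / 62.4%, or 79.4% / 74.8% if the SD is also reduced by √(1 − 0.5²) for baseline adjustment.

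The stated 80% is thus met within two points only with the ADNI SD, and under two incompatible readings: 266 per arm, or 266 in total with the extra adjustment. The wording suggests a total; the arithmetic does not settle it.

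**The case against.** The strongest reply is that this is a one-line mismatch with limited consequences. Several parts of that stand.

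- The plan foresaw a low Week 336 count and chose its detectable difference accordingly.
- Participants short of Week 336 are not discarded. SAP 7.9.3.2 fits the model to all randomized participants, so their earlier visits contribute. Censoring by enrolment date applies to both arms, so the issue is mainly precision, not bias.
- Post-lock data are not lost to reporting altogether. SAP 7.9.3.4 plans descriptive extensions of the primary spline model and the exposure model to open-label data.
- Both documents call the analysis interim, so removing the SAP clause alone would leave that word unexplained.

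A reader might infer from 266/805 that two thirds of retained participants cannot have reached Week 336 by the lock, and that the lock timing is the cause. The documents do not support this. The 266 is a planning expectation at the common close, so the shortfall it describes would remain after the timing was corrected. If 266 is per arm, the share without a Week 336 PACC is about one third. The SAP also says the sample size was set before the COVID-19 interruption.

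A reader might also try to size the loss by assuming uniform accrual and a lag between lock and close. That has no firm anchor. If 266 of 805 have reached Week 336 when the last participant reaches Week 240, the accrual span must be 96/(1 − 0.330) = 143 weeks. If instead the first participant has completed the full 204-week open-label schedule by then, the share at Week 336 is (204 − 96)/204 = 53%, not 33%.

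Finally, a reader might conclude that the analysis should wait until every participant has passed Week 336. That could take about 96 weeks after the last Week 240 visit, and under Protocol 7.1.5 visits beyond Visit 117 would need a further amendment. It would also add PACCs collected after the primary result was known. This is a trade-off, not a correction, and it is not proposed here.

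**Conclusion.** The point holds as an inconsistency with a known direction and an unknown size. SAP 5.2 carries a trigger that Protocol 6.2 and 11.2.10 do not, and SAP 7.9.3.2 does not resolve it. Followed literally, the trigger omits Week 336 PACCs collected between the lock and the common close. Including them cannot reduce the number of Week 336 observations and needs no extra assessment.

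This rests on two things taken from the documents: the common close follows the lock (Protocol 7.1.5), and the 266 is a common-close count (SAP 6.2). The number of PACCs at stake cannot be stated without the lock date, the close date and the distribution of Week 240 dates. No power loss should be quoted for it.

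**What to change.** - In SAP 5.2, delete the clause "at the time of database lock for the placebo-controlled period using data available up to 2 years in the open-label period", so that the objective matches Protocol 6.2.
- In SAP 7.9.3.2, state before unblinding that the main delayed-start analysis of the PACC is run once, with the data cut-off at the common close as Protocol 7.1.5 defines it, using every Week 336 PACC collected by then.
- If results are wanted at the placebo-controlled lock, label them descriptive.
- Align the word *interim* in Protocol 6.2 and 11.2.10 with this single analysis.
- In SAP 6.2, give the expected number of Week 336 PACCs per arm at that cut-off, and say whether 266 is a total or a per-arm figure.

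The cost is wording in both documents and an open-label result that arrives somewhat later, by the interval between the lock and the common close. No visits or procedures are added.
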